8.1 Study Endpoints

- Open label non-randomized un-blinded study to determine feasibility, safety, and efficacy.
- Feasibility endpoints;
 - Incidence of discontinuation of defibrotide. Study will be suspended if defibrotide is not tolerated as outlined below:

N (accrued)	0-6	7-12	13-18	19-24
Evaluate if discontinued in this many or more patients:	5	8	10	12

- Safety endpoints
 - Incidence of reportable SAE's (possibly drug-related and severe or unexpected). Study will be suspended if reportable AE's

N (accrued)	0-6	7-12	13-18	19-24
Evaluate if drug-related SAE's occur in this many or more patients:	4	7	10	12

- Incidence of TMA
 - Historical incidence: 7 of 22 (31.8%). With N=24, study will have 80% power to detect a statistically significant difference if incidence in this treated cohort is 8% or less.
 - Study will be re-evaluated if 2 patients develop TMA as this will render the secondary endpoint futile. May continue enrollment to determine feasibility and safety or expand the patient cohort.
- Incidence of Severe TMA
 - Historical incidence: 6 of 22 (27.3%). With N=24, study will have 70% power to detect a statistically significant difference if incidence in this treated cohort is 4% or less.
 - Study will be re-evaluated if 1 patient develops severe TMA as this will render the secondary endpoint futile. May continue enrollment to determine feasibility and safety or expand the patient cohort.

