5. I agree to maintain adequate and accurate records in accordance with CHR policies, Federal, state and local laws and regulations.

UCSF Principal Investigator / Study Chair

Printed Name

Signature

Date

Participating Site(s)

Telephone:
E-mail:

Telephone:
E-mail:

Telephone:
E-mail:

Principal Investigator

Site

Printed Name

Signature

Date

Abstract

Title	A Pilot Trial of Using Pre-Transplant Risk Stratification and Prophylactic Defibrotide to Prevent Serious Thrombotic Microangiopathy in High-Risk Hematopoietic Stem Cell Transplant Patients
Patient population	Pediatric patients age 0-30 years receiving autologous or allogeneic HSCT meeting TMA high risk criteria.
Rationale for Study	TMA is a common complication in the stem cell transplant population. Certain populations within the HSCT population are at a higher risk than others. Defibrotide is an endothelial stabilizing agent which may prevent the endothelial damage that triggers TMA in HSCT patients. The feasibility, safety, and efficacy of defibrotide prophylaxis in a pediatric transplant population is unknown.
Primary Objective	To determine the feasibility and safety of defibrotide in children receiving HSCT.
Secondary Objectives	To determine the efficacy of defibrotide prophylaxis in preventing severe TMA in pediatric patients receiving HSCT.
Study Design	Single arm non-randomized Phase II safety and feasibility trial of un-blinded defibrotide prophylaxis.
Number of patients	25
Duration of Therapy	Patients may continue treatment for 28-35 days from time of study drug initiation.
Duration of Follow up	Follow up for 6 months post-HSCT per HSCT standard of care.
Duration of study	The study will reach completion 30 months from the time the study opens to accrual.
Study Drugs	Defibrotide 6.25mg/kg IV Q6h for 28-35 days.
Safety Assessments	Weekly inpatient assessments of administration feasibility, hypersensitivity reaction, and bleeding while defibrotide is administered. This includes all HSCT SOC evaluations including routine clinical evaluations and laboratory assessments.
Efficacy Assessments	Efficacy will be based on overall incidence of TMA as well as incidence of severe TMA within 6 months post-HSCT, as defined in the protocol.

Unique Aspects of this Study	This is the first study to evaluate safety and efficacy of defibrotide in pediatric patients for prevention of severe TMA.
------------------------------	--

List of Abbreviations

AE	adverse event
ALP	alkaline phosphatase

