3.2 Number of Subjects

25 patients are expected to be enrolled.

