8.2.3 Accrual estimates

Based on historical rates we estimate accrual of 12 patients per year.

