8.3 Interim Analyses and Stopping Rules

Stopping rules as described in section 8.1.

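### The suspension limits in 8.1 are tied to patients accrued, so an event recognised just after a new band opens can fail to trigger; the tables also stop at 24

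*Combined protocol and SAP*

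**What the plan says.** Section 8.1 (Study Endpoints) gives two tables, both indexed to the number accrued.

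- **Feasibility.** The lead-in is "Study will be suspended if defibrotide is not tolerated as outlined below" and the row label is "Evaluate if discontinued in this many or more patients". The limits are 5, 8, 10 and 12 for 0-6, 7-12, 13-18 and 19-24 accrued.
- **Safety.** The lead-in breaks off after "Study will be suspended if reportable AE's". The row label is "Evaluate if drug-related SAE's occur in this many or more patients", with limits 4, 7, 10 and 12 for the same bands.

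Section 8.3 adds nothing further: "Stopping rules as described in section 8.1". No tolerable rate or error probability is given for either set of limits. The plan does not say whether they apply continuously or only at the end of a band, whether accrual waits for pending outcomes, or how a late-recognised event is counted.

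Three other statements bear on this. Section 8.2.3: "Based on historical rates we estimate accrual of 12 patients per year". The Abstract: "Patients may continue treatment for 28-35 days from time of study drug initiation". Section 3.2: "25 patients are expected to be enrolled". Section 8.2.2 also allows some patients who discontinue to be replaced.

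**The concern.** A monitoring limit should not become harder to meet merely because another patient has been enrolled whose outcome is still unknown. Here it does. Each time a band opens, the required count jumps by more than the new patient can contribute, and on the day of accrual that patient contributes nothing.

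Safety and feasibility are the primary objective (2.1), and these tables are the study's only numerical limits for them. If events are recognised with a delay, the rule followed literally can stay silent on data that would have suspended the study one accrual earlier, and more patients are then treated before it acts. Beyond 24 patients the tables give no limit at all.

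**Working it through.** **1. Limits around each band change** (8.1; percentage = limit / number accrued)

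| Accrued | Discontinuation limit | SAE limit |
|---|---|---|
| 6 | 5 (83%) | 4 (67%) |
| 7 | 8 (8/7, impossible) | 7 (100%) |
| 12 | 8 (67%) | 7 (58%) |
| 13 | 10 (77%) | 10 (77%) |
| 18 | 10 (56%) | 10 (56%) |
| 19 | 12 (63%) | 12 (63%) |
| 24 | 12 (50%) | 12 (50%) |

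The rises are 3, 2, 2 for discontinuation and 3, 3, 2 for SAEs. A count exactly at the limit at 6, 12 or 18 therefore falls below it one patient later:

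- SAE, 6 to 7: 4 or 5 events become at most 5 or 6, and 7 are needed. Even 6 of 7 (86%) does not trigger.
- Discontinuation, 6 to 7: 5 or 6 become at most 6 or 7, and 8 are needed.
- 12 to 13: 8 discontinuations become at most 9, and 7 SAE patients at most 8; 10 are needed in both tables.
- 18 to 19: 10 become at most 11, and 12 are needed in both tables.

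The limits themselves cannot be re-derived, because no design rate or error probability is stated.

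**2. Can the deciding event come after the next accrual?** Take 12 patients a year (8.2.3), 28-35 days of treatment (Abstract) and, as an assumption, Poisson accrual. The chance that the next patient is accrued during the current patient's treatment is 1 − exp(−12 × d/365):

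- d = 28: 1 − exp(−0.92) = 60%
- d = 35: 1 − exp(−1.15) = 68%

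This is the chance of overlap, not of a missed trigger. The event must also be recognised after that accrual.

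**3. Outcomes known at once.** An exact recursion gives the same chance of ever crossing whether the limits are checked after every patient or only at 6, 12, 18 and 24. For SAE rates of 40%, 50% and 60% it is 0.337, 0.676 and 0.918. Without delay the jump costs nothing.

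**4. One outcome always pending.** I simulated 200,000 trials of 24 patients, with independent outcomes at a constant assumed rate. Just after the nth accrual, n − 1 outcomes are known. As written, the limit is the one for n; indexed to evaluated patients, it is the one for n − 1. The plan's limits are unchanged. Mean enrolment counts trials that never trigger as 24.

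| Table, true rate | Measure | As written | Indexed to evaluated |
|---|---|---|---|
| SAE, 60% | Trigger by 12th accrued | 58% | 65% |
| SAE, 60% | Mean enrolment at trigger or end | 13.6 | 11.5 |
| SAE, 50% | Trigger by 12th accrued | 33% | 41% |
| SAE, 50% | Mean enrolment at trigger or end | 18.0 | 15.9 |
| SAE, 50% | Ever trigger | 63% | 68% |
| SAE, 40% | Ever trigger | 28% | 34% |
| Discontinuation, 60% | Mean enrolment at trigger or end | 16.9 | 15.3 |

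The ever-trigger figures in the last column agree with the exact values in step 3, as they should once all outcomes are known.

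**5. Coverage.** The last band ends at 24. Section 3.2 expects 25 patients, and replacement under 8.2.2 can take accrual further.

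**The case against.** The strongest reply is that the bands are meant as four looks, at 6, 12, 18 and 24 patients. The limits are then 83%, 67%, 56% and 50% for discontinuation and 67%, 58%, 56% and 50% for SAEs, which is coherent, and the anomaly disappears. A limit that cannot be reached early in a band is also ordinary: 5 cannot be reached at 4 accrued either. This stands as a possible intention, but the plan does not state it, and limits attached to ranges of accrual invite continuous use.

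A reader might infer something stronger: that enrolling patient 7 cancels a trigger already met at 6. The documents do not support that. Section 8.1 suspends the study when a limit is met, so a limit recognised at 6 accrued has acted before patient 7 enters. The gap is confined to events recognised after the next band opens.

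Other oversight also limits the consequence. Section 7.7 provides monthly review of adverse events and ongoing review of serious suspected reactions, and 5.1.1 has rules for individual patients. Neither supplies the missing study-level trigger.

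The difference between suspending in the lead-in and evaluating in the row label is a minor point. Section 7.1 combines a pause with an evaluation as one action, so the two words need not conflict.

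**Conclusion.** The point holds as a gap in specification, not as an arithmetic error in the limits. Read literally, the tables can miss or delay a trigger when the deciding event among the first 6, 12 or 18 patients is recognised after the next patient is accrued. The stated accrual rate and treatment length make that plausible.

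In the modelled case, accrual indexing costs about two extra patients at SAE rates of 50-60% (18.0 − 15.9 = 2.1; 13.6 − 11.5 = 2.1). For discontinuation at 60% it costs about one and a half (16.9 − 15.3 = 1.6). At a 40% SAE rate it lowers the chance of ever triggering by 6 percentage points.

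These figures are upper-end. They assume that one outcome is pending at every accrual, whereas the overlap estimate is 60-68% and some events occur early in treatment. The event rates are assumptions too. With outcomes known at once there is no loss. The absence of a limit beyond 24 patients needs no modelling.

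**What to change.** In 8.1, keep the limits and change how they are applied:

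1. Index both tables to patients evaluated, meaning that treatment and the safety window in 7.5 are complete or the event has already occurred. Say how this applies to tandem-transplant patients, who repeat the schedule (6.1).
2. State that a limit met by the patients in a band stands until reviewed, whatever the later accrual.
3. Extend the last band to the final N, covering patient 25 and any replacements.
4. Complete the safety lead-in so that it states the same action as the feasibility table.

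Limits for each patient, interpolated through the plan's own points, are an option and not part of the correction. They would tighten the rule within bands, and with no stated target rate or error probability there is nothing to judge them against.

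The cost is a short amendment to 8.1 and slightly more reviews at moderate event rates. Sample size is unaffected.

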1.3 Rationale for the Proposed Study

Upon retrospective review of our cases of TMA and the medical literature, we are now classifying patients as either standard-risk for the development of TMA, or high-risk, based on the following clinical criteria:

1. Patients undergoing tandem autologous transplant with thiotepa in one or more of the conditioning regimens.

OR:

2. Patients with at least 3 of the following characteristics:
 - a) >10 years of age
 - b) Non-Caucasian race/ Hispanic ethnicity
 - c) Undergoing haploidentical transplant
 - d) Minor ABO Mismatch

Using these criteria, we retrospectively reviewed 160 transplants performed from 1/1/13 to 9/30/16. There were 13 cases of TMA total (8.1%), with 7 cases (4.4%) deemed severe by the onset of renal failure, development of pericardial effusion, and/or death. In the 138 standard-risk patients, there were 6 total cases of TMA, but only 1 was severe (0.7%). Conversely, in the 22 high-risk patients there were 7 total TMA cases, 6 of which were severe (27.3%). Most cases showed evidence of evolving TMA before Day +100 post-HCT, and some cases of TMA were evident within a week following HCT.

Several groups have demonstrated that the onset of endothelial injury and clinical TMA typically begins within 4-6 weeks following HCT (Jodele Blood Rev 2015, Obut BMT 2016). Therefore, the hypothesis is that in high-risk patients the administration of certain combinations of high-dose conditioning agents (radiation and/or chemotherapy) and/or post-HSCT inflammatory events initiate the complement pathway to aberrantly attack the endothelium. Although the current standard treatment for post-transplant microangiopathic processes involves targeting inflammatory mediators with complement blockade and plasmapheresis, these therapies do not address the prevention or treatment of the initial pathologic trigger, namely, endothelial damage.

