7.4.2.3 Serious

An adverse event or suspected adverse reaction is considered *serious* if, in the view of either the investigator or sponsor (The University of California, San Francisco), it results in any of the following outcomes:

- Death
- Life-threatening adverse event
- Inpatient hospitalization or prolongation of existing hospitalization
- A persistent or significant incapacity or substantial disruption of the ability to conduct normal life function
- Congenital anomaly/birth defect

Important medical events that may not result in death, are life-threatening, or require hospitalization may be considered serious when, based upon appropriate medical judgment, they may jeopardize the patient or subject and may require medical or surgical intervention to prevent one of the outcomes listed in this definition. Examples of such medical events include allergic bronchospasm requiring intensive treatment in an emergency room or at home, blood dyscrasias or convulsions that do not result in inpatient hospitalization, or the development of drug dependency or drug abuse.

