7.5 Recording of an Adverse Event

All grade 3 and above adverse events will be entered into the study database, whether or not the event is believed to be associated with use of the study drug. Safety data (SAEs) will be collected from the time of admission until the day after completion of defibrotide (6-12 times the half-life of the study drug). Data about these events and their severity will be recorded using the NCI CTCAE v4.0.

The Investigator will assign attribution of the possible association of the event with use of the investigational drug, and this information will be entered into the study database using the classification system listed below:

Relationship	Attribution	Description
Unrelated to investigational drug/intervention	Unrelated	The AE is clearly NOT related to the intervention
	Unlikely	The AE is doubtfully related to the intervention
Related to investigational drug/intervention	Possible	The AE may be related to the intervention
	Probable	The AE is likely related to the intervention
	Definite	The AE is clearly related to the intervention

Signs or symptoms reported as adverse events will be graded and recorded by the Investigator according to the CTCAE. When specific adverse events are not listed in the CTCAE they will be graded by the Investigator as *none, mild, moderate* or *severe* according to the following grades and definitions:

- Grade 0 No AE (or within normal limits)
- Grade 1 Mild; asymptomatic or mild symptoms; clinical or diagnostic observations only; intervention not indicated
- Grade 2 Moderate; minimal, local, or noninvasive intervention (e.g., packing, cautery) indicated; limiting age-appropriate instrumental activities of daily living (ADL)
- Grade 3: Severe or medically significant but not immediately life-threatening; hospitalization or prolongation of hospitalization indicated; disabling; limiting self-care ADL
- Grade 4: Life-threatening consequences; urgent intervention indicated
- Grade 5: Death related to AE

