7.7 Adverse Events Monitoring

All adverse events, whether or not unexpected, and whether or not considered to be associated with the use of the study drug, will be entered into the study database, as noted above.

The Investigator will assess all adverse events and determine reportability requirements to the UCSF's Institutional Review Board, the Committee on Human Research (CHR).

All adverse events entered into the study database will be reviewed by the Study Committee on a monthly basis. The Study Committee will review and discuss at each meeting the selected toxicity, the toxicity grade, and the attribution of relationship of the adverse event to the administration of the study drug(s).

All grade(s) 3-5 adverse events entered into the study database will be reviewed on a monthly basis at the Study Committee meetings. The Site Committee will review and discuss the selected toxicity, the toxicity grade, and the attribution of relationship of the adverse event to the administration of the study drug(s).

In addition, all suspected adverse reactions considered "serious" entered into the study database, will be reviewed and monitored by the study committee on an ongoing basis and discussed at study meetings, which take place every eight weeks.

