7.8 Expedited Reporting

Reporting to the Data and Safety Monitoring Committee

If a death occurs during the treatment phase of the study or within 30 days after the last administration of the study drug(s) and it is determined to be related either to the study drug(s) or to a study procedure, the Investigator or his/her designee must notify the study Chair (or qualified alternate) within 1 business day of knowledge of the event. The contact may be by phone or e-mail.

Reporting to UCSF Committee on Human Research (Institutional Review Board)

The Principal Investigator must report events meeting the UCSF CHR definition of "Unanticipated Problem" (UP) within 10 business days of his/her awareness of the event.

Expedited Reporting to the Food and Drug Administration

If the study is being conducted under an IND, the Sponsor-Investigator is responsible for determining whether or not the suspected adverse reaction meets the criteria for expedited reporting in accordance with Federal Regulations (21 CFR §312.32).

The Investigator must report in an IND safety report any suspected adverse reaction that is both serious and unexpected. The Sponsor-Investigator needs to ensure that the event meets all three definitions:

- Suspected adverse reaction (as defined in 6.1.30)
- Unexpected (as defined in 0)
- Serious (as defined in 6.1.5)

If the adverse event does not meet all three of the definitions, it should not be submitted as an expedited IND safety report.

The timeline for submitting an IND safety report to FDA is no later than **15 calendar days** after the Investigator determines that the suspected adverse reaction qualifies for reporting (21 CFR 312.32(c)(1)).

Any unexpected fatal or life-threatening suspected adverse reaction will be reported to FDA no later than **7 calendar days** after the Investigator's initial receipt of the information (21 CFR 312.32(c)(2)).

Any relevant additional information that pertains to a previously submitted IND safety report will be submitted to FDA as a Follow-up IND Safety Report without delay, as soon as the information is available (21 CFR 312.32(d)(2)).

Reporting to Pharmaceutical Companies providing Study Drug

- Reporting to Jazz Pharmaceuticals

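### The 8.1 safety rule has no separate trigger for a drug-related death, states no SAE rate it guards against, and the committee subsection of 7.8 sends related-death notices only to the study Chair

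*Combined protocol and SAP*

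**What the plan says.** Section 8.1 defines the safety endpoint as "Incidence of reportable SAE's (possibly drug-related and severe or unexpected") and says the study will be suspended on that basis, although the sentence is unfinished. The limits are in a table labelled "Evaluate if drug-related SAE's occur in this many or more patients": 4 for 0-6 accrued, 7 for 7-12, 10 for 13-18 and 12 for 19-24. A parallel table for discontinuation of defibrotide has limits of 5, 8, 10 and 12. Section 8.3 adds no further stopping rule and refers back to 8.1.

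Section 7.4.2.3 calls an event serious if "it results in any of the following outcomes". Death heads that list, and prolonged hospitalization is also on it. Section 7.5 sets the collection window: "Safety data (SAEs) will be collected from the time of admission until the day after completion of defibrotide".

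Section 7.8, in its subsection on reporting to the Data and Safety Monitoring Committee, deals with deaths during treatment or within 30 days of the last dose that are judged related to study drug or a study procedure. For these, "the Investigator or his/her designee must notify the study Chair (or qualified alternate) within 1 business day of knowledge of the event". The signature page has one line for "UCSF Principal Investigator / Study Chair". The committee's membership and powers are not described.

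**The concern.** Safety is half of the primary objective, and section 2.1 names bleeding risk as one of its two components. A safety rule for an agent that may increase bleeding should say what happens after a death attributed to it. Here a fatal event and a prolonged admission carry equal weight, and the rule acts only on the total.

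Two features add to this. A related death after SAE collection has closed may not reach the total at all. And the subsection that appears to bring in a monitoring committee does not say that the committee receives anything or decides anything. If related deaths occurred, the protocol would not oblige anyone to pause enrolment and would not identify an independent body to advise on continuing.

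Separately, the limits come without a target rate, error probability or method. A reader cannot tell what level of drug-related SAEs they are meant to detect, or how reliably.

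**Working it through.** **Inputs.** SAE limits 4/7/10/12 and discontinuation limits 5/8/10/12 (8.1); N = 24 (8.1, 8.2); SAE window (7.5); related-death window (7.8); treatment through Day +21 (3.4, 5.1). The plan gives no operating characteristic for the table, so there is no stated figure to reproduce.

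**1. Deaths against the tables.** Suppose three of the first six patients die of drug-related causes and the other three have no drug-related SAE and stay on drug. The SAE count is 3 < 4. If the deaths also count as discontinuations, that count is 3 < 5. Neither table triggers. At every stage the discontinuation limit is at least as high as the SAE limit (5 vs 4, 8 vs 7, 10 vs 10, 12 vs 12), so it gives no earlier stop for a run of related deaths.

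**2. Windows.** For a patient treated through Day +21, SAE collection ends on Day 21 + 1 = +22. The 7.8 window runs to Day 21 + 30 = +51. A related death from Day +23 to Day +51 (29 days) falls under the 7.8 notice but outside the SAE window that feeds 8.1.

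**3. What passes the table.** The highest non-triggering counts are 3 of 6, 6 of 12, 9 of 18 and 11 of 24. The last is 11/24 = 45.8%, provided the earlier limits were also respected. The limits as fractions at the end of each band are 4/6 = 67%, 7/12 = 58%, 10/18 = 56% and 12/24 = 50%.

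**4. Chance of ever triggering.** Let p be the true probability that a patient has a drug-related SAE, and let b(n) be the limit in force at n accrued. For k < b(n), the probability of k affected patients with no trigger so far is

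f(n, k) = (1 − p) f(n−1, k) + p f(n−1, k−1), with f(0, 0) = 1.

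Mass reaching k ≥ b(n) is removed and added to the trigger probability.

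First band by hand at p = 0.40: P(at least 4 of 6) = 15(0.4⁴)(0.6²) + 6(0.4⁵)(0.6) + 0.4⁶ = 0.1382 + 0.0369 + 0.0041 = 0.179. Carrying the recursion on gives 0.242 by N = 12, 0.274 by N = 18 and 0.337 by N = 24.

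| True drug-related SAE rate | P(ever triggers by N = 24) |
|---|---|
| 20% | 1.9% |
| 25% | 4.8% |
| 27.3% | 7.0% |
| 30% | 10.4% |
| 40% | 33.7% |
| 45% | 50.5% |
| 50% | 67.6% |
| 60% | 91.8% |

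The result is the same to three decimals whether the table is checked after every patient or only at 6, 12, 18 and 24.

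**5. Deaths alone.** If related deaths were the only counted events and their true rate were 20%, about 24 × 0.20 = 4.8 deaths would be expected. The table would trigger with probability 1.9%.

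**The case against.** The strongest reply is that the plan has more safety oversight than the 8.1 table, and most of that reply is correct.

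- Deaths are not ignored. Death is a listed serious outcome, so a related death within the SAE window counts. What is missing is a separate trigger.
- A reader might infer from 7.8 that related deaths are reported only to the Chair. They are not. The supplier receives all SAEs that require collection and reporting within 1 business day. FDA receives unexpected fatal suspected reactions within 7 calendar days if there is an IND. The IRB receives Unanticipated Problems within 10 business days. Participating sites have their own PIs, so notifying the Chair is not always self-notification. None of these routes, however, is tied to an enrolment pause.
- A reader might take the words "discussed at study meetings, which take place every eight weeks" in 7.7 to mean that serious reactions are reviewed less often than other events. That discussion is additional: 7.7 already has the Study Committee review all recorded events monthly, and serious suspected reactions on an ongoing basis. So SAEs below the limits are not unreviewed, and nothing says that continuation rests with the PI alone. The Study Committee's membership is not given, so its independence is not shown either way.
- Later deaths may still be recorded. Table 6.1 schedules AE assessment through week 24, and 7.5 records all events of grade 3 and above. But the 8.1 count is of SAEs, and the documents do not say that an event after the SAE window is added to it.
- The documents give no unacceptable SAE rate, so every rate in the table of trigger probabilities is a reviewer's choice. That is true, and it is part of the point.

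**Conclusion.** The point stands in this form: 8.1 has no separate trigger for death, related deaths after the SAE window may escape its count, and no independent committee is shown to receive the notice that 7.8 places under the committee's name. Three related deaths in the first six patients require no pause, provided that at most one further patient discontinues and no other patient has a drug-related SAE. This rests on reading the two 8.1 tables literally.

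The table's sensitivity is modest: at a true rate of 40% it fails to trigger about two times in three (1 − 0.337 = 0.663). These probabilities assume independent patients with a common rate. The rates are illustrative and not the plan's. Whether such limits are acceptable cannot be judged until the plan says what rate they guard against.

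A reader might go further and set the 11 patients against 24 × 6/22 = 6.5 severe TMA cases expected at the historical rate, concluding that tolerated harm exceeds any possible benefit. The documents do not support that. A drug-related SAE may be a prolonged admission, while section 1.1 reports mortality as high as 80% in severe TMA, so the two are not exchangeable one for one. The 95% interval for 6/22 (10.7% to 50.2%) corresponds to 2.6 to 12.1 of 24 patients, which includes 11. The historical severe cases were also defined differently (1.3) from 7.2.2.

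**What to change.** 1. Add to 8.1: any death within the 7.8 window judged possibly, probably or definitely related to defibrotide (the 7.5 attribution categories) pauses enrolment until the Data and Safety Monitoring Committee named in 7.8 has reviewed it. Because this acts on the death itself, it also closes the gap between the two windows.
2. In 7.8, send the 1-business-day notice to that committee as well as to the Chair, and have the committee advise on resumption. The protocol should say who sits on it, since no membership is described.
3. Beside the 8.1 table, state the drug-related SAE rate it is meant to guard against and the chance of triggering at that rate. Complete the unfinished sentence above the table at the same time.

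The cost is protocol wording and use of a committee the plan already names. The downside is a possible short enrolment pause after a related death. These are trial-level rules and leave individual patients' treatment unchanged.

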8.2.1 Sample Size and Power Estimate

Assuming an historical rate of severe TMA of 28%, alpha=5%, and N=24, power to detect a statistically significant value of 4% in this cohort is 92%. The minimum number of patients to enroll to achieve 80% power to detect a difference, assuming a 4% incidence in this cohort, is N=19. Assuming a sample size of N=24, the study has 80% power to detect a statistically significant difference if the incidence of severe TMA in this treated cohort is <5%. Given the small sample size, adjustments for multiple comparisons will not be made.

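### Section 8.1 calls the TMA comparisons futile at 1 severe case or 2 cases overall; taken literally, that caps power at 38% and 42%, against stated powers of 70% (92% in 8.2.1) and 80%

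*Combined protocol and SAP*

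**What the plan says.** Section 8.1 takes its historical rates from 22 high-risk controls: 7 with TMA (31.8%) and 6 with severe TMA (27.3%).

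- For any TMA: "With N=24, study will have 80% power to detect a statistically significant difference if incidence in this treated cohort is 8% or less". Then: "Study will be re-evaluated if 2 patients develop TMA as this will render the secondary endpoint futile".
- For severe TMA: "With N=24, study will have 70% power to detect a statistically significant difference if incidence in this treated cohort is 4% or less". Then: "Study will be re-evaluated if 1 patient develops severe TMA as this will render the secondary endpoint futile".
- After either trigger: "May continue enrollment to determine feasibility and safety or expand the patient cohort".

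Section 8.2.1 takes a historical severe rate of 28%, alpha of 5% and N=24, and says that "power to detect a statistically significant value of 4% in this cohort is 92" percent. It adds: "The minimum number of patients to enroll to achieve 80% power to detect a difference, assuming a 4% incidence in this cohort, is N=19".

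Section 8.3 consists of "Stopping rules as described in section 8.1". Section 7.1 has its own TMA rule: a pause and a futility evaluation once there are more than 2 cases. Section 8.4.3 says that incidence will be compared with historical controls but names no test, and 8.1 and 8.2.1 name none either.

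**The concern.** A count that makes an endpoint futile is a count at which significance is out of reach. Power is the probability of staying below that count. The futility counts and the power figures are therefore two statements about the same rejection region, and here they do not match.

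A check by hand shows it. The expected number of severe cases at the design rate is 24 × 0.04 = 0.96, and of TMA cases 24 × 0.08 = 1.92. The counts called futile, 1 and 2, are about what would be seen if the drug worked exactly as hypothesised.

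Either the study team would write off the efficacy comparison at counts that the power statement treats as success, or readers are given a power about twice what the futility counts allow. Severe TMA is also the endpoint on which 8.2.1 justifies the sample size. Separately, 7.1 and 8.1 differ on when the TMA comparison is in doubt.

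**Working it through.** **Inputs.** From 8.1: N=24; controls 6/22 severe and 7/22 TMA; design rates 4% and 8%; futility counts 1 and 2; stated powers 70% and 80%. From 8.2.1: historical rate 28%, alpha 5% with sidedness not given, stated power 92%, minimum N of 19.

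**Reproducing the plan's figures.** The one-sample normal approximation has power Φ[(|p0−p1|√n − z√(p0(1−p0))) / √(p1(1−p1))]. Take p0=0.28, p1=0.04 and two-sided z=1.96:

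- n=24: (1.176 − 0.880)/0.196 = 1.51, power 93.4%. With p0=6/22 it is 91.4%. The stated 92% lies between.
- n=19: (1.046 − 0.880)/0.196 = 0.85, power 80.2%. At n=18 it is 76.0%. This matches the stated minimum of 19.

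So 8.2.1 looks like a test against a fixed historical rate. No single formula tried gives both powers in 8.1. A one-sample, one-sided formula using the null variance gives 80.5% for TMA but 82.0% for severe TMA. A two-sample, one-sided pooled formula gives 71.6% for severe TMA but 65.8% for TMA.

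**The cap implied by the futility counts.** If count c defeats the comparison, power is at most P(X ≤ c−1):

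- Severe TMA, c=1: P(0 of 24 at 4%) = 0.96^24 = 0.3754.
- TMA, c=2: P(≤1 of 24 at 8%) = 0.92^24 + 24 × 0.08 × 0.92^23 = 0.1352 + 0.2821 = 0.4173.

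The triggers therefore fire at the design rates with probability 1 − 0.3754 = 62% and 1 − 0.4173 = 58%. To reach the stated powers under these counts, the true rate would have to be about 1.5% (for 70%) or 0.35% (for 92%) for severe TMA, and about 3.4% (for 80%) for TMA.

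**What each candidate test gives.** The 22 controls are held at their observed counts. Power is P(X below the first non-significant count), with P(X≤0, 1, 2) = 37.5%, 75.1%, 93.1% at 4% and P(X≤1, 2, 3) = 41.7%, 69.9%, 87.9% at 8%. For the one-sample normal test, power comes from the formula above. The p-values are for the last significant and the first non-significant count.

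| Test | Severe: first non-significant count (p-values) | TMA: first non-significant count (p-values) | Power, severe / TMA | Statements that fail |
|---|---|---|---|---|
| One-sample exact, one-sided 5% | 3 (0.023, 0.075) | 4 (0.028, 0.080) | 93% / 88% | Both counts, the 70%, the N=19 |
| One-sample normal, two-sided | 3 (0.037, 0.104) | 4 (0.042, 0.111) | 91–93% / 83% | Both counts, the 70% |
| Fisher, two-sided | 2 (0.043, 0.128) | 2 (0.020, 0.066) | 75% / 42% | Severe count, the 92%, the TMA 80% |
| Chi-square, uncorrected | 2 (0.029, 0.091) | 3 (0.045, 0.113) | 75% / 70% | Both counts, the 92%, the TMA 80% |
| Chi-square, Yates | 1 (0.021, 0.077) | 2 (0.037, 0.102) | 38% / 42% | All stated powers |

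In the first row, N=19 fails because the exact test against 28% first reaches 80% power at N=15 (success at ≤1, p=0.0495, power 88.1%; at N=14 it is 56.5%).

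**Letting the control count vary.** With 22 controls drawn at 6/22 or 7/22, two-sided power (severe / TMA) is 60% / 50% for Fisher, 63% / 56% for uncorrected chi-square and 46% / 38% for Yates. None reaches 70%, 80% or 92%.

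**7.1 against 8.1.** Section 7.1 acts at the third TMA case. Section 8.1, which 8.3 names as the source of the stopping rules, declares futility at the second.

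**The case against.** The caps depend on a literal reading. The trigger is a non-binding re-evaluation, so no stopping action limits power. The plan allows true rates below 4% and 8%, where the caps are higher, and allows the cohort to grow, which changes N. All of that is right. But 8.1 states as fact that the endpoint will be futile at these counts, and its power claims must hold at the edge of the range it gives, which is 4% and 8% with N=24.

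Sidedness is not stated, and one-sided two-sample tests do better. With the control count varying, a one-sided uncorrected test has power 76% for severe TMA and 69% for TMA, so the 70% in 8.1 is attainable. It still misses the TMA 80% and the severe 92%. With the observed controls, halving the two-sided p-values makes 2/24 severe (0.045) and 2/24 TMA (0.022) significant, so both futility counts fail there too. A one-sample exact test at 2.5% gives TMA power of 70% instead of 88%, and again contradicts both counts.

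The counts may have another origin: 1/24 = 4.2% and 2/24 = 8.3% are the first observed rates above the design rates. That is a guess. If it is right, it explains the error but does not make those counts futile.

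The two TMA rules can both be carried out, with a re-evaluation at 2 cases and a pause at 3. That also stands; the disagreement is only about when the comparison counts as lost. And TMA is a secondary endpoint in a pilot whose primary aim is safety and feasibility.

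**Conclusion.** The concern holds. At N=24, at the design rates and given the observed controls, the futility counts in 8.1 allow at most 37.5% power for severe TMA (stated 70% in 8.1 and 92% in 8.2.1) and 41.7% for TMA (stated 80%). The counts and the powers cannot both be right. The 70% and the 92% also disagree with each other for nearly the same scenario (27.3% against 28% historical).

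Which side is wrong depends on the test. Only Yates among those tried supports both counts, and then every stated power fails. The fixed-rate test that best fits 8.2.1 makes 1/24 severe and 2/24 TMA clear successes.

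This should be fixed but does not threaten the trial. The 62% and 58% are chances of a re-evaluation, not of stopping, and the primary safety and feasibility boundaries are not affected.

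**What to change.** 1. In 8.4.3, name one test and its sidedness for the comparison with historical controls.
2. From that test, derive the futility counts in 8.1 and the power statements in 8.1 and 8.2.1, including the minimum N, and restate power where it falls. Use one historical severe rate in both sections.
3. Unless the chosen test supports it, delete the statement that 1 severe case or 2 TMA cases makes the endpoint futile.
4. Make the TMA count in 7.1 match 8.1.
5. If a one-sample test is chosen, say that it treats the rate in 22 historical patients as known.

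The cost is wording in 7.1, 8.1, 8.2.1 and 8.4.3, and possibly a lower stated power. No extra patients or procedures are needed.
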